6.1.2 Guidelines for continuation of treatment

For guidelines for dose modification of treatment, refer to [Section 6.2](#).

Patients who have RECIST-defined PD by investigator assessment, but who, in the opinion of the investigator, have evidence of continued clinical benefit from LDK378 may continue to receive the study medication. In such cases, these patients must continue to be followed for safety assessments as per the schedule of assessments, but imaging assessments will no longer be required.

6.1.3 Treatment duration

Patients should continue LDK378, and should follow the protocol safety assessments as scheduled, until they experience any of the following:

- Disease progression (radiologically documented according to RECIST 1.1 by the investigator assessment) with the exception of patients, who, in the investigator's judgment, continue to show evidence of clinical benefit despite RECIST-defined PD (see [Section 6.1.2](#))
- Unacceptable toxicity that precludes further treatment.
- Start of a new anti-cancer therapy.
- Pregnancy
- Treatment is discontinued at the discretion of the investigator or patient.
- Lost to follow-up
- Death
- Study terminated by Sponsor

Patients who permanently discontinue the study drug for any reason other than disease progression must, if consenting to further follow-up, continue efficacy follow-up assessments as scheduled in the protocol until the time of confirmed disease progression or death.

After discontinuing LDK378, further treatment for NSCLC is left to the physician's discretion.

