Study design	This is a phase I/II, open-label, multi-center study in which the pharmacokinetics, safety, tolerability and efficacy of LDK378 will be assessed in adult Chinese patients with locally advanced or metastatic NSCLC harboring a confirmed ALK rearrangement. The study includes a phase I component for the first 15 patients (5 day PK run-in period) and a phase II component for all the patients with continuous dosing. Patients must have demonstrated progression during or after crizotinib treatment whether or not previously treated with cytotoxic chemotherapy and have no available ALK-targeted treatment options. Approximately 100 patients will be enrolled. For the first 15 patients enrolled in this study, patients will have an additional 5-day PK run-in period before treatment period. The pharmacokinetics profile of LDK378 in Chinese adult patients with ALK-rearranged NSCLC will be evaluated. Additional patients may be enrolled in the study with PK run-in period in case PK profiles from some of the enrolled patients are deemed not evaluable due to early discontinuation from the study or due to vomiting events on the day of PK sampling. Treatment with LDK378 750 mg qd will continue until the patient experiences unacceptable toxicity that precludes further treatment, discontinues treatment at the discretion of the investigator or patient, starts a new anti-cancer therapy and/or dies. LDK378 may be continued beyond RECIST-defined PD if, in the judgment of the investigator, there is evidence of clinical benefit. Patients who discontinue the study medication in the absence of progression will continue to be followed for tumor assessment until the time of PD.
Population	Chinese adult patients with ALK-rearranged locally advanced or metastatic NSCLC that has progressed during or after crizotinib therapy no matter whether or not previously treated with cytotoxic chemotherapy.

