After the PK run-in period, the treatment period for the first 15 patients will start on Cycle 1 Day 1 in which LDK378 will be given as continuous daily oral dosing at 750 mg QD in 28-day cycles. Apart from these 15 patients, the rest of the enrolled patients will start treatment with LDK378 at 750 mg QD on Cycle 1 Day 1 in 28-day cycles as phase II component of the study.

Data from all patients entering the 28-day cycles treatment period will be used to characterize the PK profile, safety and tolerability of LDK378 as continuous 750 mg once daily dose as well as to demonstrate the antitumor activity of LDK378 as measured by ORR by investigator assessment.

[figure not shown]
[figure not shown]

Figure 4-1 Study Design

Patients will take LDK378 once daily, at approximately the same time each day in the morning. On days when a PK sample is obtained, the patient will take LDK378 during the clinic visit as instructed by the study staff. Treatment with LDK378 will continue until the patient experiences unacceptable toxicity that precludes further treatment, discontinues treatment at the discretion of the patient or investigator, starts a new anti-cancer therapy or dies. Clinical and laboratory assessments will be performed as described in [Section 7](#). If the patient experiences RECIST-defined progressive disease (PD) on LDK378 as assessed by the investigator, treatment with the study drug may be continued if, in the judgment of the investigator, there is still evidence of clinical benefit. These patients will be counted as PD for ORR, DOR, DCR and PFS calculations.

Tumor response will be evaluated every 8 weeks (i.e. every 2 cycles) starting from the first day of treatment with LDK378 until the time of RECIST-defined PD by investigator assessment, withdrawal of consent for further follow-up, loss to follow-up or death. This schedule of tumor assessment must continue regardless of dose interruptions. In patients who discontinue treatment in the absence of progression, tumor assessments will continue every 8 weeks until progression of disease, withdrawal of consent for further follow-up, loss to follow-up or death.

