7.1.5 Discontinuation of study treatment

A patient will be defined as on the study if they are continuing to have any study data collected, i.e. if the patient is being treated with LDK378, is in efficacy follow-up after discontinuing LDK378, or is in survival follow-up.

Patients may voluntarily withdraw from study treatment for any reason at any time. In this situation, the patient should be encouraged to consent to be followed for tumor assessments until the development of Progressive Disease (as assessed by investigator) and/or survival. If a patient decides to discontinue from the study treatment, the investigator must make every effort (e.g. telephone, e-mail, letter) to determine the primary reason for this decision and

record this information in the patient's chart and on the appropriate CRF pages. They may be considered withdrawn if they state an intention to withdraw, fail to return for visits, or become lost to follow-up for any other reason.

The investigator should discontinue study treatment for a given patient if, on balance, he/she believes that continuation would be detrimental to the patient's well-being.

Patients must permanently stop the study treatment if one of the following occurs:

- Pregnancy
- Study Terminated by Sponsor
- Patient/guardian decision
- Physician decision
- Lost to follow-up
- Death

Patients may permanently stop the study treatment for one of the following reasons:

- Progression of disease (radiological as assessed by investigator)
- AEs
- Non-compliance with study treatment
- Technical Problems
- Use of prohibited treatment
- - Any protocol deviation that results in a significant risk to the patient's safety

Patients who become pregnant during the trial must be withdrawn ([Section 8.4](#)). Patients who become pregnant must cease all tumor assessments regardless of whether or not they developed Progressive Disease.

Patients who discontinue study treatment during the treatment phase should NOT be considered withdrawn from the study. They should be scheduled for a visit as soon as possible and within 7 days after the last dose of study treatment, at which time all of the assessments listed for the EOT visit will be performed. If a patient withdraws from treatment at a study visit, EOT assessments do not need to be repeated. An End of Treatment Phase Disposition eCRF page should be completed, giving the date and reason for stopping LDK378 treatment.

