Patients who have RECIST-defined PD by investigator assessment, but who, in the opinion of the investigator, have evidence of continued clinical benefit from LDK378 may continue to receive this drug. These patients will continue assessments as detailed in [Table 7-1](#) except tumor and [REDACTED]. In such cases, patients must complete the EOT visit only after permanent discontinuation of LDK378. An End of Treatment Phase Disposition eCRF page should be completed, giving the date and reason for stopping the study treatment.

At a minimum, all patients who discontinue study treatment, including those who refuse to return for a final visit, will be contacted for safety evaluations during the 30 days following the last dose of study treatment.

If patients refuse to return for these visits or are unable to do so, every effort should be made to contact them or a knowledgeable informant by telephone to determine the survival status.

[REDACTED]

[REDACTED]

[REDACTED]

[REDACTED]

Patients who discontinue study treatment should be considered withdrawn from the study after the final visit assessments are performed or when it is clear that the patient will not return for these assessments. They may be considered withdrawn if they state an intention to withdraw, fail to return for visits, or become lost to follow-up for any other reason.

If a patient discontinues study treatment, but continues study assessments, (e.g. during post treatment follow up phase as detailed in [Table 7-1](#)), the patient remains on study until such time as he/she completes protocol criteria for ending study assessments. At that time, the reason for study completion should be recorded on the End of Post Treatment (Study Phase Completion) Disposition eCRF page.

If using IRT, the Investigator must contact the IRT to register the subject's discontinuation from treatment.

Patients who discontinue study treatment should enter the survival follow-up period or continue tumor assessments when appropriate. Tumor assessments will continue until the investigator assessment determined disease progression, patient withdraws consent from tumor assessments patient is lost to follow-up, death or study terminated by Sponsor.

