7.1.7.2 Post-Treatment Follow-up

All patients who discontinued treatment during the treatment phase for reasons other than death, lost to follow-up, pregnancy or disease progression as per investigator assessment (Section 7.1.3) will continue tumor and [REDACTED] as per Table 7-1 (every 8 weeks) thereafter until PD as per investigator assessment, withdrawal of consent or death. Once the patient ceases tumor follow-up, the reason for completion should be recorded on the End of Post Treatment Disposition (Study Phase Completion) eCRF page.

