Tumor assessments will be done until RECIST-defined PD by investigator assessment, death, lost to follow-up, or patient decision involving withdrawal of consent.

If a patient discontinues study treatment in the absence of PD, tumor assessments will continue to be done every 8 weeks until RECIST-defined PD by investigator assessment, death, lost to follow-up, or patient decision involving withdrawal of consent.

If a patient continues treatment with LDK378 after RECIST-defined PD by investigator assessment, no further imaging assessments on study are required.

Imaging evaluations will also be performed at the End of Treatment (EOT) visit. If a patient is known to have PD at a scheduled study visit, EOT imaging evaluations do not need to be repeated for the EOT visit.

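### Sections 6.1.3 and 7.2.1.2 of the protocol keep tumor imaging going after a stop for pregnancy, which 7.1.5 forbids and 7.1.7.2 exempts

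*Protocol*

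**What the plan says.** **Text that continues imaging**

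- Protocol 6.1.3 gives a list of events that end LDK378 treatment. Pregnancy is a separate entry. Below the list comes the rule: "Patients who permanently discontinue the study drug for any reason other than disease progression must, if consenting to further follow-up, continue efficacy follow-up assessments", with confirmed progression or death as the end point.
- Protocol 7.2.1.2, on how long imaging lasts, ends tumor assessments at progression, death, loss to follow-up or withdrawal of consent. It adds: "If a patient discontinues study treatment in the absence of PD, tumor assessments will continue to be done every 8 weeks". On the EOT visit it says: "Imaging evaluations will also be performed at the End of Treatment (EOT) visit". The one relief it gives is for a patient already known to have progressed.
- Protocol 7.1.5 requires the full set of EOT assessments from anyone who stops treatment. Near its end it gives a list of reasons for ending tumor assessments, and pregnancy is not on it.

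**Text that stops imaging**

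- Protocol 7.1.5: "Patients who become pregnant must cease all tumor assessments regardless of whether or not they developed Progressive Disease".
- Protocol 7.1.7.2 applies post-treatment tumor follow-up to patients who stopped treatment "for reasons other than death, lost to follow-up, pregnancy or disease progression as per investigator assessment".

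**Overview text.** The protocol summary ("Patients who discontinue the study medication in the absence of progression will continue to be followed for tumor assessment until the time of PD"), section 4.1 ("In patients who discontinue treatment in the absence of progression, tumor assessments will continue every 8 weeks until progression of disease") and SAP 2.4 repeat the general rule without the exception.

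**The concern.** Sections 6.1.3 and 7.1.5 are both mandatory, and for one type of patient they point in opposite directions. Which one a site follows depends on which section it opens. Section 7.2.1.2 is where a reader would look up when imaging ends, and it sides with 6.1.3.

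The scans are CT or MRI of chest and abdomen, and 7.2.1.1 prefers CT with intravenous contrast. The protocol gives no reason for stopping imaging in pregnancy, but fetal safety is the evident one. Following 6.1.3 or 7.2.1.2 literally would send a pregnant patient for scans that 7.1.5 prohibits. Following 7.1.5 would depart from 6.1.3. Section 12 allows no authorized deviations. Section 12.1 permits immediate safety action, but accepts that such action may itself count as a deviation.

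**Working it through.** No figure is involved, so the check is to follow one patient through the text. She consents to follow-up, becomes pregnant on LDK378, stops for that reason and has not progressed.

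| Protocol section | Applies to her? | Instruction on tumor imaging |
|---|---|---|
| 6.1.3 | Yes: pregnancy is a listed stopping reason and is not progression | Continue to progression or death |
| 7.2.1.2, duration | Yes: stopped without progression | Continue every 8 weeks |
| 7.2.1.2, EOT visit | Yes: not known to have progressed | Image at EOT |
| 7.1.5, EOT visit | Yes: stopped treatment | Do all EOT assessments |
| 7.1.5, pregnancy rule | Yes, by name | Stop all tumor assessments |
| 7.1.7.2 | Exempt, by name | No post-treatment tumor follow-up |

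Two phrases might reconcile these.

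1. Section 6.1.3 refers to assessments as the protocol schedules them. That governs timing. The sentence sets its own scope (every reason except progression) and its own end point. Deferring to Section 7 would not settle the matter either, because 7.2.1.2 and 7.1.7.2 disagree within it.
2. Section 8.4 says a patient who becomes pregnant must be withdrawn, and 7.1.5 cross-refers to it. Neither says whether that means from treatment or from the study. Section 7.1.5 also says that stopping treatment is not withdrawal from the study. So 8.4 does not clearly end imaging.

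No order of precedence between sections was found. The conflict therefore stands in current operative text.

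**How many patients.** The Amendment 3 rationale gives 103 treated, 66 off treatment and 37 still on treatment at 29-Sep-2015 (66 + 37 = 103). The Amendment 2 rationale says recruitment is complete. So 103 is the ceiling, men included. The 37 is a ceiling only for those then on drug, since some of the 66 could still be in tumor follow-up and the 7.1.5 rule is not limited to patients on drug. The number of women of childbearing potential is not given. Exclusion criterion 16 requires highly effective contraception during the study and for 3 months after stopping, and 7.2.2.5.4 repeats urine pregnancy tests at each cycle and at EOT. The true number should be far below the ceiling.

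**Analysis.** A patient whose imaging stops without an event is already covered: SAP 3.2.10.2 censors progression-free survival and duration of response at the last adequate tumor assessment.

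**The case against.** The best defense is that the protocol largely resolves this itself. The pregnancy rule in 7.1.5 is specific and absolute, 7.1.7.2 is the operative section for post-treatment tumor follow-up, and a site managing a pregnancy would turn to 8.4 or 7.1.5. The scope of 6.1.3 also cannot be literal, because its own list includes death, loss to follow-up and termination by the sponsor, none of which can lead to further scans. This shows the intent, and the specific rule would probably be followed. It does not remove the conflict. Scans after death are impossible, whereas scans in pregnancy are possible and 6.1.3 requires them. The site is left to infer which section governs.

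A reader might count every sentence without the exception as a contradiction. That goes too far. The summary, 4.1 and SAP 2.4 are overviews, and leaving a rare exception out of an overview matters little. In 7.1.5 itself, "Patients who discontinue study treatment should enter the survival follow-up period or continue tumor assessments when appropriate" is qualified and needs no edit. The qualifier does not reach the following sentence, which lists when tumor assessments end, nor the EOT sentence that comes just after the pregnancy rule.

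On EOT imaging, 7.1.5 gives one more relief: assessments need not be repeated if the patient stops at a study visit. That narrows the EOT conflict without closing it. Table 7-1 is only partly readable in the public copy, so any note there could not be checked.

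**Conclusion.** The inconsistency is real and worth correcting. Sections 6.1.3 and 7.2.1.2 require imaging that 7.1.5 forbids and 7.1.7.2 exempts. It is a drafting conflict on a safety instruction; no design decision is in question. The number affected is small: at most 103 patients, men included, and probably very few.

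Two stronger readings are not supported. A reader might infer that pregnant patients will in practice be scanned, but the protective rule is already mandatory and would probably prevail. A reader might also infer that the efficacy results are at risk. ORR, the sample size and the censoring rules are unaffected.

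The conclusion assumes that the intent is to stop imaging in pregnancy, as 7.1.5 and 7.1.7.2 both indicate, and that no part of Table 7-1 that cannot be read already states the exception.

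**What to change.** - **6.1.3:** change the exception to read *other than disease progression or pregnancy*.
- **7.2.1.2:** add pregnancy to the end points in the general duration sentence and in the 8-weekly sentence, and exempt pregnant patients from EOT imaging.
- **7.1.5:** add *except tumor imaging in pregnancy* to the EOT-visit sentence, and add pregnancy to the later list of reasons for ending tumor assessments. The pregnancy rule itself stays as it is.
- **Optional:** align the protocol summary, 4.1 and SAP 2.4.

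The cost is wording in three sections, six sentences in all (1 in 6.1.3, 3 in 7.2.1.2, 2 in 7.1.5), with no new data and no change to the analysis. It can go into the next amendment. Amendment 2 made the same kind of edit when it changed the reasons for ending tumor assessments across 4.1, 7.1.5, 7.1.7.2 and 7.2.1.2.

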6.1.4 Definition of treatment cycle

A treatment cycle is defined as 28 calendar days from the start of treatment with LDK378 (Day 1, cycle 1) for the purposes of scheduling procedures and evaluations.

6.2 Dose modifications

6.2.1 Dose modification and dose delay

For patients who do not tolerate the protocol-specified dosing schedule, dose adjustments are permitted in order to allow the patient to continue the study treatment. Any changes in LDK378 administration must be recorded on the Dosage Administration Record eCRF.

General guidelines for dose modifications for toxicities other than those listed in Table 6-3.

For grade 1 and tolerable grade 2 treatment-related toxicities, patients may continue at the current dose of study treatment. For intolerable grade 2 treatment-related toxicities, dosing should be interrupted until resolution to grade 1 or lower followed by dose reduction to the next dose level.

For grade 3 or grade 4 treatment-related toxicity that is not considered by the investigator to be life-threatening, patients should interrupt study treatment until resolution to grade 1 or lower; then study treatment may continue following a dose reduction to the next dose level, if, in the opinion of the Investigator, the patient continues to experience clinical benefit. For any grade 3 or 4 treatment-related toxicity that is considered by the investigator to be life-threatening, permanently discontinue study treatment.

More detailed LDK378 dose modification guidelines are described in [Section 6.2.3.](#) for selected toxicities. Any planned variance from these guidelines in view of patient safety must first be discussed with the sponsor unless there is an urgent need for action.

All dose modifications, interruptions or discontinuations must be based on the worst preceding toxicity as graded by the NCI Clinical Toxicity Criteria (NCI-CTCAE version 4.03).

6.2.2 Treatment interruption and treatment discontinuation

If the administration of LDK378 is temporarily interrupted for reasons other than toxicity, then treatment with LDK378 may be resumed at the same dose. The same applies if the patient experiences an unacceptable toxicity not specifically described in [Table 6-3](#) or [Section 6.2.2](#), provided this toxicity resolved to \leq CTCAE grade 1.

If the treatment with LDK378 is withheld due to toxicity, scheduled visits and all assessments should continue to be performed (with the exception of the dosing of the withheld study drug), as described in [Table 7-1](#).

If the treatment with LDK378 dosing is withheld for more than 28 consecutive days (counting from the first day when a dose was missed), due to toxicity, then LDK378 should be permanently discontinued except in cases where the investigator believes the patient continues to derive clinical benefit. In such cases, treatment with LDK378 may be resumed at a lower dose.

Patients who discontinue the study due to a study drug related AE or an abnormal laboratory value must be followed as described in [Section 6.2.4](#).

All patients will be followed for safety until 30 days after the last dose of LDK378. Patients whose treatment is temporarily interrupted or permanently discontinued due to an AE or abnormal laboratory value must be followed until resolution or stabilization of the event, whichever comes first, including all study assessments appropriate to monitor the event.

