- Table 1-3, Table 1-4 and Table 1-5 have been removed
- Section 4.1, Section 7.1.5, Section 7.1.7.2, and Section 7.2.1.2.; “Start of a new anti-cancer therapy” was removed from the list of allowable reasons to stop collection of tumor assessments.
- Section 4.3: the definition of the end of the study has been updated
- Section 6.2.1: sub-title has been updated to specify that guidelines are related to toxicities other than those listed in Table 6-3

- Section 6.2.4.8: added new section ‘Guidelines for the follow-up of laboratory pancreatic abnormalities’
- Table 6-3: updated with criteria for dose modification and dose delay of LDK378 treatment for renal, pancreatic and cardiac toxicity
- Table 6-4: updated instructions on follow-up evaluations in case of pancreatic toxicity
- Section 6.3.1.2: updated bisphosphonates use and interaction with LDK378
- Section 6.3.1.5: updated with LDK378 dosing guidance in association to radiotherapy and surgical resection in order to align with program level language
- Section 6.3.1.6: updated to align with program level language
- Section 6.3.2.6: clarification that concomitant use of medications that are CYP2C9 and CYP3A4/5 substrates with narrow therapeutic index is not permitted with LDK378
- Table 7.1: Protocol sections numbers have been updated
- Section 7.1.5: section renamed ‘discontinuation of study treatment’. Content of Sections 7.1.5.1 and 7.1.5.1.1 added to Section 7.1.5. Sections 7.1.5.1 is now ‘replacement policy’. Discontinuation of study treatment and withdrawal have been clarified.
- Section 7.1.6: added new section ‘withdrawal of consent’. Consequently section ‘Follow up period’ and related subsections were renumbered.
- Section 7.1.7.4: definition of lost to follow up has been clarified
- Table 7-3: Lipase has been added to blood chemistry
- Section 8.1.3: adverse events of special interest have been clarified
- Section 3 Table 3-1, Section 10.4.1.1 and Table 10-1: PK parameters have been clarified
- Section 10.5.3: added clarification for “on-treatment period”.
- Section 10.8: details of the interim analysis have been clarified
- Editorial and typographical changes throughout the document as required

IRB/IEC

A copy of this amended protocol will be sent to the Institutional Review Board (IRBs)/Independent Ethics Committee (IECs) and Health Authorities.

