Total Bilirubin** (for patients with Gilbert Syndrome these dose modifications apply to changes in direct [conjugated] bilirubin only)	
Grade 1 ($> ULN$ and $\leq 1.5 \times ULN$)	Maintain dose level with liver function test (LFTs)*** monitored as per protocol
Grade 2 (> 1.5 and $\leq 3.0 \times ULN$) with ALT or AST $\leq 3.0 \times ULN$	Omit dose until resolved to \leq Grade 1, then: If resolved in ≤ 7 days, then maintain dose level If resolved in > 7 days, then $\downarrow 1$ dose level
Grade 3 (> 3.0 and $\leq 10.0 \times ULN$) with ALT or AST $\leq 3.0 \times ULN$	Omit dose until resolved to \leq Grade 1, then: If resolved in ≤ 7 days, $\downarrow 1$ dose level If resolved in > 7 days discontinue patient from LDK378

Worst toxicity (CTCAE 4.03 Grade)*		Dose Modifications for LDK378
Grade 4 ($> 10.0 \times \text{ULN}$)		Permanently discontinue patient from LDK378
AST or ALT		
Grade 1 ($> \text{ULN}$ and $\leq 3.0 \times \text{ULN}$)		Maintain dose level with LFTs*** monitored per protocol
Grade 2 (> 3.0 and $\leq 5.0 \times \text{ULN}$) without total bilirubin elevation to $> 2 \times \text{ULN}$		Maintain dose level with LFTs*** monitored per protocol
Grade 3 (> 5.0 and $\leq 20.0 \times \text{ULN}$) without total bilirubin elevation to $> 2 \times \text{ULN}$		Omit dose until resolved to \leq Grade 1, then $\downarrow 1$ dose level
Grade 4 ($> 20.0 \times \text{ULN}$) without total bilirubin elevation to $> 2.0 \times \text{ULN}$		Omit dose until resolved to \leq Grade 1, then $\downarrow 1$ dose level
AST or ALT and concurrent Total bilirubin		
AST or ALT $> 3.0 \times \text{ULN}$ with total bilirubin $> 2.0 \times \text{ULN}$ in the absence of cholestasis or hemolysis		Permanently discontinue patient from LDK378 Refer to Section 6.2.4.2 for additional follow-up
PANCREATIC		
Amylase and/or lipase elevations (in the absence of clinical symptoms)		
Grade 1 ($> \text{ULN}$ and $\leq 1.5 \times \text{ULN}$)		Maintain dose level
Grade 2 ($> 1.5 - 2.0 \times \text{ULN}$)		Maintain dose level
Grade ≥ 3 ($> 2.0 \times \text{ULN}$)		Omit dose until resolved to \leq Grade 1, then $\downarrow 1$ dose level
Note: Withhold ceritinib for acute onset of new or progressive unexplained abdominal symptoms, such as severe pain or vomiting; perform diagnostic procedures (e.g., abdominal CT scan or ultrasound) to exclude pancreatic pathology.		
RENAL		
Serum creatinine		

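### Sections 6.2.1 and 6.2.2 give different restart doses for treatment-related toxicities outside Table 6-3, and in one narrow band Table 6-3 keeps dosing the worse of two liver profiles

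*Protocol*

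**What the plan says.** **Restart dose.** Section 6.2.1 carries the subtitle "General guidelines for dose modifications for toxicities other than those listed in Table 6-3". For intolerable grade 2 treatment-related toxicity, "dosing should be interrupted until resolution to grade 1 or lower followed by dose reduction to the next dose level". Grade 3 or 4 treatment-related toxicity that is not life-threatening follows the same pattern: hold to grade 1 or lower, then continue one level down.

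Section 6.2.2 first lets treatment interrupted for reasons other than toxicity restart at an unchanged dose, and then extends this to some toxicities: such treatment "may be resumed at the same dose. The same applies if the patient experiences an unacceptable toxicity not specifically described in" two listed places. The exclusion and its condition read "not specifically described in [Table 6-3](#) or [Section 6.2.2](#), provided this toxicity resolved to", with the threshold set at grade 1 or lower.

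**Liver rows of Table 6-3 (multiples of ULN).**
- Bilirubin grade 2 (above 1.5, up to 3.0) is an omit row, but only "with ALT or AST" at or below 3.0.
- AST/ALT grade 2 (above 3.0, up to 5.0) is a maintain row, provided it is "without total bilirubin elevation to" above 2.
- AST/ALT grades 3 and 4 (above 5), with the same bilirubin limit, are omit-then-reduce rows.
- AST or ALT above 3.0 with bilirubin above 2.0 is a permanent stop, except with cholestasis or hemolysis.

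**The concern.** Sections 6.2.1 and 6.2.2 cover the same events, set the same resolution threshold and prescribe different restart doses. A site that follows 6.2.2 as printed is following the protocol. The choice has lasting consequences, because Section 6.2.3 forbids re-escalation and allows at most three modifications.

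In Table 6-3 a higher transaminase value can switch off the bilirubin hold without triggering any stricter rule, so the patient with the worse liver profile stays on drug.

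Safety comes first here. A secondary effect falls on tolerability, which belongs to a primary objective and is summarized through dose reductions and interruptions (Protocol 10.5.3.5; SAP 3.2.5). Those counts, and the times to first reduction and first interruption, would partly reflect which rule a site applied.

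**Working it through.** **Part 1: the two rules side by side**

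| | Section 6.2.1 | Section 6.2.2 |
|---|---|---|
| Toxicity | Outside Table 6-3, treatment-related | Outside Table 6-3 and outside 6.2.2; no limit on causality |
| Resolution needed | Grade 1 or lower | Grade 1 or lower |
| Restart | One level lower | Same dose permitted |

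The 6.2.2 exclusion names 6.2.2, so it removes nothing that 6.2.1 governs. The overlap concerns holds of up to 28 days. After a longer hold for toxicity, 6.2.2 itself requires discontinuation or, where benefit continues, a lower dose.

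Size per event, from Table 6-2:
- 750 to 600 mg: (750 - 600)/750 = 20%
- 600 to 450 mg: (600 - 450)/600 = 25%
- 450 to 300 mg: (450 - 300)/450 = 33%
- At 300 mg no lower level exists, so one rule leads to permanent discontinuation and the other to continued dosing.

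The territory is not empty. Decreased appetite (34.1%, all grades) and hypokalemia (4.3%, grade 3/4) appear in Table 1-1 and have no Table 6-3 row. It is not the main territory either. Of the seven AEs that most often led to adjustment or interruption (Section 1.2.1.2.1), six have their own rows. The seventh, abdominal pain, is partly covered by a withhold note in the pancreatic rows, which gives no restart dose.

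**Part 2: liver profiles run through the rows**

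The bilirubin rows' ALT-or-AST condition has two readings: A, neither enzyme above 3; B, at least one enzyme at or below 3. The Gilbert and indirect-bilirubin exceptions are left out. Values are multiples of ULN.

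| TBIL | ALT | AST | Cholestasis or hemolysis | Reading A | Reading B |
|---|---|---|---|---|---|
| 1.8 | 2 | 2 | No | Omit | Omit |
| 1.8 | 4 | 2 | No | Maintain | Omit and maintain both match |
| 1.8 | 4 | 4 | No | **Maintain** | **Maintain** |
| 1.8 | 6 | 2 | No | Omit, reduce | Omit, reduce (grade 3 governs) |
| 2.5 | 4 | 2 | No | Stop | Omit and stop both match |
| 2.5 | 4 | 4 | No | Stop | Stop |
| 2.5 | 4 | 2 | Yes | No row | Omit |
| 2.5 | 4 | 4 | Yes | No row | No row |

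Rows 1 and 3 show the reversal under either reading. The worst-toxicity footnote does not help at 1.8/4/4, because only the maintain row matches and both abnormalities are grade 2.

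A grid of 253,440 profiles without cholestasis or hemolysis (TBIL 1.1 to 12.0 by 0.1; ALT and AST 1.5 to 25 by 0.5) compared each profile with the same TBIL at ALT 2 and AST 2. Every weaker action for a worse profile lay at TBIL 1.6 to 2.0. Under A the higher enzyme was 3.5 to 5.0; under B both enzymes were. On a continuous scale this is TBIL above 1.5 to 2.0 with AST/ALT above 3 to 5.

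The band can be reached from a permitted baseline. Section 5.2 admits patients with liver metastasis at AST and ALT below 5 x ULN with TBIL below 1.5 x ULN, so a bilirubin rise alone is enough.

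**The case against.** **The restart conflict is a slip.** Probably so. Reading 6.2.1 for 6.2.2 in the exclusion largely removes it. The amendment history points the same way: for Section 6.2.1, "sub-title has been updated to specify that guidelines are related to toxicities other than those listed in Table 6-3". The texts could also be reconciled by keeping 6.2.2 for toxicity not related to treatment, but 6.2.2 states no such limit. In addition, "Any planned variance from these guidelines in view of patient safety must first be discussed with the sponsor" unless action is urgent; a site relying on 6.2.2 need not see itself as varying from anything. Intent is therefore fairly clear, but the printed instruction is still wrong.

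**The liver band is narrow and watched.** This stands. Section 6.2.4.2 requires weekly liver tests from grade 2. Crossing TBIL 2.0 triggers the permanent stop (absent cholestasis or hemolysis), and crossing 5 x ULN triggers omit and reduce. Section 7.1.5 tells the investigator to stop when treatment is detrimental. None of these requires a hold inside the band.

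**Matching both omit and maintain is not a contradiction.** A reader might infer one at 1.8/4/2 under reading B. The table gives an action per toxicity, and a maintain for one does not cancel an omit for another: grade 2 diarrhea is omit, grade 2 nausea is maintain, and a patient with both would be held. This is a clarity point only.

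**No matching row does not mean no instruction.** Treatment-related profiles with no row could fall back on 6.2.1. That is arguable, but the table should not leave it to inference.

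**Conclusion.** Both defects are in the current text and should be corrected. The first is a one-level difference in restart dose for treatment-related toxicities outside Table 6-3. The second is a reversal confined to TBIL above 1.5 to 2.0 x ULN. It is certain when both transaminases are above 3 to 5 x ULN; if the bilirubin row means that neither enzyme may exceed 3, one such enzyme is enough.

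Three stronger inferences are not supported:
- **A share of patients or events affected.** Table 1-1 lists only terms with at least 10% incidence, regardless of drug relationship. It omits grade 3/4 hyperglycemia (5.5%) and lipase increase (5.1%), both of which have Table 6-3 rows. The documents give no frequency for the liver band.
- **A general failure of the liver rules.** Outside the band, without cholestasis or hemolysis, no reversal appears.
- **Damage to a test or to the accuracy of the tables.** Protocol 10.10 plans no formal testing, and SAP 4.1.6 counts doses actually taken. The tables would describe correctly what was given; only the rule behind the counts would vary by site.

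**What to change.** 1. In Section 6.2.2, change the reference to Section 6.2.1, or limit the sentence to toxicity not related to treatment.
2. In Table 6-3, delete the transaminase condition from the bilirubin grade 2 and 3 rows. The hold then applies at any transaminase level unless the permanent-stop row applies. Tie its release to bilirubin at grade 1 or lower, since some patients with liver metastasis enter with raised transaminases.
3. Limit the AST/ALT grade 2 maintain row to TBIL at or below 1.5 x ULN.
4. State that the stricter action governs when more than one row applies.
5. Align the cholestasis-or-hemolysis exception with Section 6.2.4.2, which excepts cholestasis only.

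With these changes, all three 1.8 profiles with transaminases up to 4 are held, 1.8/6/2 is omit and reduce, both 2.5 profiles without cholestasis or hemolysis stop, and both with it are held. Changing ALT or AST to ALT and AST would not be enough: with cholestasis, 2.5/4/2 would then fall in no row.

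One drafting detail remains. With cholestasis or hemolysis, TBIL above 2 to 3 and AST/ALT above 5 would get only the bilirubin grade 2 hold, which allows the same dose after 7 days or less, whereas TBIL 1.8 with ALT 6 is reduced. Letting the AST/ALT grade 3 and 4 rows apply at any TBIL, under item 4, closes this.

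The cost is one cross-reference and a few row wordings in an amendment, plus a site letter. No new assessments, patients or SAP changes are needed. Recruitment was complete, and 37 of 103 treated patients were still on drug at Amendment 3, so the benefit is to those patients.
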